### ***Bayesian Estimation and Statistical Evaluation of Hypothesis:***

Superiority of the Test lens relative to the pre-defined threshold with respect to unacceptable lens fitting will be evaluated using Bayesian statistics. The null and alternative hypotheses for evaluating superiority of the Test lens relative to 90% are as follows:

$$H_0: p_T \leq 0.90$$

$$H_A: p_T > 0.90,$$

where  $p_T$  is the probability of event (i.e., proportion of subjects to achieve optimization in 4 lenses or less while wearing the test lens). Based on Bayesian posterior probability distribution of the proportion  $p_T$ , superiority is interpreted as 95% probability of the Test lens being statistically greater than the pre-defined threshold of 90% (i.e.,  $p_T > 0.90$ ) with respect to

# Clinical Study Protocol

## Johnson & Johnson Vision Care, Inc.

unacceptable lens fitting rate. If the upper bound of the 95% central posterior credible interval is above 0.90, it can be concluded that there is 95% probability that the Test lens is superior to the 90% threshold (statistically better) based on the observed sample.

In the case of all eyes have an acceptable lens fit (i.e., zero event of non-optimization), a Bayesian hierarchical model accounting for zero event problem will be considered. Details of this model will be provided in the stand-alone SAP.

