# Clinical Study Protocol

## Johnson & Johnson Vision Care, Inc.

### 14.2. Sample Size Justification

This study was designed and powered to test for superiority of the Test lens after 1-week of optimized lens wear with respect to the following: binocular HLHC visual performance at distance, intermediate and near, subjective Vision scores for both the hyperopic and myopic groups grade 3 or higher slit lamp findings and unacceptable lens fitting. Additionally, this study was also powered to test for superiority with respect to CLUE Comfort and Handling and Lens Fit success.

The sample size for co-primary efficacy endpoints was estimated to achieve a minimum statistical power of 99% for visual performance and CLUE Vision using a 2-sided type I error rate of 1%. Co-primary safety endpoints (slit lamp findings and unacceptable lens fitting) were estimated to achieve a minimum statistical power of 90% with 95% central posterior credible interval. The sample size for secondary endpoints (with the exception of lens fit success) were estimated to achieve a minimum statistical power of 80% using a two-sided type I error rate of 1% each. a minimum statistical power of 80% for lens fit success with the 99% central posterior credible interval.

With respect to safety endpoints, historical data from 7 studies were utilized, however, for primary efficacy and secondary endpoints historical data from only two studies were utilized in the sample size calculation since there were the only studies that have completed after design-lock (Phase2b). A summary of historical studies utilized in the sample size calculation are summarized in Table 6 below. For the sample size estimate for this study, only data from period 1 was utilized. Table 7 below summaries the historical data by endpoint.

Table 6: Historical Studies Utilized for Sample Size Calculations

Study Number	Design	Population	Number Enrolled	Number in Safety Population	Number in PP population	Endpoints utilized for sample size
[REDACTED]	2x2	Myopes	34	33	30	Primary Safety
	2x2	Hyperopes	48	44	41	Primary Safety
	2x3	Hyperopes	81	78	67	Primary Safety
	2x3	Myopes	71	68	60	Primary Safety
	2x3	Hyperopes	78	75	64	Primary Safety, Efficacy, Secondary
[REDACTED]	2x3	Myopes	81	78	66	Primary Safety, Efficacy, Secondary
[REDACTED]	2 Phase 3x3	Hyperopes	40	37	34	Primary Safety

PP: Per-Protocol

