# Clinical Study Protocol

## Johnson & Johnson Vision Care, Inc.

=5%). All co-primary safety and co-primary efficacy hypotheses must be met to test any secondary hypotheses.

*Secondary hypotheses* (except for lens fit success) will be tested with using an overall two-sided family-wise type I error rate of 5% (1% individually). Lens fit success will be tested using a 99% credible interval.

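### Lens-fit success: Section 14.6 declares superiority when the upper 95% credible bound exceeds 90%, so a lens truly at 90% would pass 96–98% of the time; the power calculation used the lower 99% bound

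*Combined protocol and SAP*

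**What the plan says.** Section 2.3 (secondary hypothesis 5) and Section 14.6 (Number of Lenses Required to Achieve Optimization) test whether more than 90% of subjects reach their optimum pair in four lenses or fewer. Section 14.6 writes H0: p_T ≤ 0.90 against H_A: p_T > 0.90, with p_T defined as the "proportion of subjects to achieve optimization in 4 lenses or less while wearing the test lens".

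The decision sentence opens with this condition: "If the upper bound of the 95% central posterior credible interval is above 0.90, it can be concluded". What it then draws from a pass is a probability statement, worded as follows: "there is 95% probability that the Test lens is superior to the 90% threshold". Just before it, "superiority is interpreted as 95% probability of the Test lens being statistically greater than the pre-defined threshold of 90" percent.

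The rest of the plan differs on bound and level:

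- Section 14.2, general text: "a minimum statistical power of 80% for lens fit success with the 99% central posterior credible interval".
- Section 14.2, Lens Fit Success: each simulated trial passed if the **lower** bound of the 99% interval was above 90%.
- Section 14.4: "Lens fit success will be tested using a 99% credible interval".

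Two further phrases in Section 14.6 belong to a different endpoint. Superiority "with respect to unacceptable lens fitting will be evaluated using Bayesian statistics", and the zero-event provision begins "In the case of all eyes have an acceptable lens fit (i.e., zero event of non-optimization".

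**The concern.** To support p_T > 0.90, the whole credible interval must lie above 0.90, so its lower bound must exceed 0.90. The rule as written looks at the other end. It fails a lens only when the data show it to be below 90%, which makes passing the default.

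There are four separate faults in the same paragraph:

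- **Bound.** Section 14.6 uses the upper bound; the power simulation in Section 14.2 used the lower.
- **Level.** Section 14.6 uses 95%; Sections 14.2 and 14.4 use 99%.
- **Meaning.** A pass is described as 95% probability of exceeding 90%, but the rule needs only more than 2.5%.
- **Unit and endpoint.** The hypothesis is per subject. The power simulation assumed a left–right eye correlation of 0.70, the analysis model is for correlated binary data, and the zero-event sentence speaks of eyes and acceptable fit.

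Lens-fit success is part of the secondary objective in Section 2.1 and is formally tested. Section 14.10 says the analysis will follow these sections. Applied literally, the rule would produce a superiority statement that the data need not support.

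**Working it through.** **Inputs.** Threshold 0.90 (Section 14.6). Planning rate 98%, eye correlation 0.70, stated n = 92 and power 82.1% (Section 14.2, Lens Fit Success and Table 8). Completers 100, enrolled up to 120 (Section 14.2). No prior is given for this endpoint. The only one printed is N(0,1000) on the logit coefficients with beta(0.5, 0.5) on the correlation, for the slit-lamp model in Section 14.5. I therefore show three priors on p: that logit-normal prior, Jeffreys beta(0.5, 0.5) and uniform beta(1, 1).

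**Step 1: which rule does the plan's own power match?** Take the two-eye model of Section 14.5 with correlation ρ:

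P(both succeed) = (1−ρ)p² + ρp; P(one succeeds) = 2(1−ρ)p(1−p); P(neither) = (1−ρ)(1−p)² + ρ(1−p).

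With n = 92, p = 0.98, ρ = 0.70 and the lower 99% bound, enumeration of the possible outcomes gives power 88.7% (logit-normal), 83.7% (Jeffreys) and 78.9% (uniform). The stated 82.1% lies inside that range. It cannot be reproduced exactly because the prior used is not stated, and I do not dispute it. The upper-95% rule gives power of about 100%, so 82.1% cannot have come from it.

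**Step 2: what each rule means.** Upper bound of a central 95% interval above 0.90 ⇔ P(p > 0.90 | data) > 2.5%. Lower bound of a central 99% interval above 0.90 ⇔ P(p > 0.90 | data) > 99.5%.

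**Step 3: operating characteristics, subject level, n = 100.** Find the smallest passing count x, then P(declare) = P(X ≥ x) with X ~ Bin(100, p).

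| | Logit-normal | Jeffreys | Uniform |
|---|---|---|---|
| **Upper 95% rule (Section 14.6)**: passes from | 84 | 84 | 85 |
| P(p > 0.90 given data) at that count | 3.7% | 2.9% | 4.3% |
| P(declare), true 90% | 97.9% | 97.9% | 96.0% |
| P(declare), true 85% | 67% | 67% | 57% |
| P(declare), true 80% | 19% | 19% | 13% |
| **Lower 99% rule (Section 14.2)**: passes from | 97 | 97 | 98 |
| P(declare), true 90% | 0.8% | 0.8% | 0.2% |
| P(declare), true 98% | 85.9% | 85.9% | 67.7% |

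An observed 84% success rate, below the threshold, would therefore be declared superior to 90% under two of the three priors.

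**Step 4: does sample size or unit matter?** At true 90%, subject level, the upper-95% rule passes 96.1–98.0% of the time at n = 92 and 97.0–98.4% at n = 120. In the two-eye model at n = 100 (ρ = 0.70), it passes about 98.2%, 97.6% and 96.9% at true 90%, and 64%, 60% and 56% at true 85%, in the same prior order. The lower-99% rule in that model passes 1.2%, 0.7% and 0.4% at true 90%.

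**Step 5: correcting only the bound.** The lower 95% bound at n = 100 requires 96 successes under all three priors, and P(declare) at 90% is 2.4%. That direction is right, but the level still conflicts with Section 14.4.

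**The case against.** The best defence is that this is an obvious slip with little practical consequence. H_A, the closing words of the decision sentence and the simulation in Section 14.2 all show the intended direction. The wording appears carried over from Primary Safety Hypothesis 2 in Section 14.5, where the upper bound is correct because that hypothesis is p < 0.05. The endpoint is secondary and is tested only after all co-primary hypotheses pass. Historical success was 100%, and at 98–100% the rule as written passes anyway. The 96–98% also presumes a true rate of exactly 90% and literal programming of the sentence.

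All of that stands as a limit on impact, but it does not rescue the sentence. The sentence is complete, it is the operative rule, and only the zero-event model is deferred to the stand-alone SAP.

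Three narrower objections also have merit:

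- The 95%-versus-99% mismatch is not peculiar to this endpoint. The CLUE and logMAR tests in Sections 14.5 and 14.6 also print 95% intervals against a 1% level.
- The Section 14.5 prior is not stated to apply here, so results under it are an assumption. At subject level with n = 92, it lets the lower-99% rule pass from 89, with a 1.45% false-declaration rate at 90%, above the nominal 0.5% tail.
- Secondary analyses use the intent-to-treat population, so n may exceed 100. At n = 120, subject-level power at 98% under the lower-99% rule is 90.6% (logit-normal, Jeffreys) or 78.0% (uniform).

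**Conclusion.** The concern holds. The rule in Section 14.6 contradicts its own alternative hypothesis, its own probability statement, and the bound and level in Sections 14.2 and 14.4. If the test is reached and the rule is applied as written, a lens truly at 90% is declared superior in 96.0–97.9% of trials of 100 subjects, and in 96–98.4% across the sample sizes, priors and units examined. Under the lower-99% rule the corresponding figure is between 0.2% and about 1.5%.

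The size of the error does not depend materially on the unassigned prior or on whether subjects or eyes are analysed. Power under the corrected rule does depend on both. No primary conclusion is at risk, but a pass under the rule as written would not support the lens-fit claim, so the text must be corrected before it is used.

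**What to change.** In Section 14.6, and in the stand-alone SAP before database lock:

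1. Declare superiority only if the lower limit of the 99% central credible interval for p_T exceeds 0.90.
2. Replace the 95% probability interpretation with a posterior probability of at least 99.5%, since a central 99% interval leaves 0.5% below its lower limit.
3. Replace the references to unacceptable or acceptable fit with optimization in four lenses or fewer, including in the zero-event sentence.
4. State whether the unit is the subject (as in Section 2.3) or the eye (as in the power simulation), and which prior applies.
5. If the unit is the subject, restate power with its prior. At a true 98% and the lower 99% bound, the logit-normal prior gives 88.7% at n = 92 and 85.9% at n = 100; Jeffreys gives 72% and 86%; uniform gives 72% and 68%.

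The cost is wording only. No new data are needed, and the bound and level become those already used for sample size. Under the Section 14.5 prior the sample size can stand with either unit (88.7% at n = 92 for subjects and for eye pairs, against the 80% minimum). Under Jeffreys or uniform at subject level, n = 92 falls short at 72%, which is why the prior should be stated.

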### 14.7. Other Exploratory Analysis

A meta-analysis will be performed on individual items from the study questionnaire utilizing data from all historical studies with database hard-lock, completed after design-lock [Phase 2b]. This will include [REDACTED]. The approximate number of subjects expected from the historical data is approximately 213. The allocation of subjects by study is displayed in Table 9.

Table 9: Clinical Studies Planned to be Utilized in Exploratory Meta-Analysis

Study Number	Population Included	Approximate Allocation of Subjects
[REDACTED]	Hyperopes	75
[REDACTED]	Myopes	78
[REDACTED]	Hyperopes	60

[REDACTED] is currently in execution

Any analyses performed on exploratory endpoints will be on the intent-to-treat population. Statistical analysis will follow the Meta-Analysis approach as discussed in Whitehead. This analysis will be discussed completely in the stand-alone SAP.

The stand-alone SAP will include full details describing the following:

1. Specific items from questionnaire to be included
2. Historical data to be utilized
3. Structure for grouping questions assessing similar areas of performance (e.g., comfort or vision)
4. Methodology for assessing associations between endpoints within a grouping
5. Model details to be utilized for each grouping
6. Strategy for adjustments for multiple testing
7. Strategies regarding utilizing subject data, if a subject participate in more than 1 historical study
8. Methodology for accounting for different study designs

This planned exploratory meta-analysis is intended to support stand-alone claims for the JJVC Investigational Multifocal Contact Lenses manufactured in senofilcon A C3.

# Clinical Study Protocol

## Johnson & Johnson Vision Care, Inc.

### 14.8. Interim Analysis

There will not be an interim analysis performed on this study.

### 14.9. Procedure for Handling Missing Data and Drop-Outs

Missing or spurious values will not be imputed. The count of missing values will be included in the summary tables and listings.

Subject dropout is expected to be one of the main reasons of missing data in this clinical trial. Past clinical trials don't provide the evidence that subject dropout is systematic or not-at-random. To evaluate the impact of missing data, sensitivity analysis will be conducted using multiple imputation methods if the proportion of subject dropout is greater than the 10%. The SAS/STAT procedures PROC MI and PROC MIANALYZE will be utilized with a parametric regression method used to make at least 50 imputations.

### 14.10. Procedure for Reporting Deviations from Statistical Plan

The analysis will be conducted according to that specified in above sections. There are no known reasons for which it is planned to deviate from these analysis methods. If for any reason a change is made, the change will be documented in the study report along with a justification for the change.

## 15. DATA HANDLING AND RECORD KEEPING/ARCHIVING

### 15.1. Electronic Case Report Form/Data Collection

The data for this study will be captured on electronic case report forms (eCRFs) using the BioClinica EDC system. An authorized data originator will enter study data into the eCRFs using the EDC system. Data collected on equipment that is not captured in EDC will be formatted to the specification of the JJVC database manager and sent to JJVC for analysis.

External data sources for this study include: Not Applicable

The clinical data will be recorded on dedicated eCRFs specifically designed to match the study procedures for each visit. Only specifically delegated staff can enter data on a CRF. Once completed, the eCRFs will be reviewed for accuracy and completeness and signed by the Investigator. The sponsor or sponsor's representatives will be authorized to gain access to the subject recordation for the purposes of monitoring and auditing the study.

Edit checks, electronic queries, and audit trails are built into the system to ensure accurate and complete data collection. Data will be transmitted from the clinical site to a secure central database as forms are completed or updated, ensuring information accuracy, security, and confidentiality. After the final database lock, the Investigator will be provided with Individual Patient Profiles (IPP) including the full audit trail on electronic media in PDF format for all of the study data. The IPP must be retained in the study files as a certified copy of the source data for the study.

# Clinical Study Protocol

## Johnson & Johnson Vision Care, Inc.

The content and structure of the eCRFs are compliant with ISO14155:2020. Error! Reference source not found.

### 15.2. Subject Record

At a minimum, subject record should be available for the following:

- subject identification
- eligibility
- study identification
- study discussion
- provision of and date of informed consent
- visit dates
- results of safety and efficacy parameters as required by the protocol
- a record of all adverse events
- follow-up of adverse events
- medical history and concomitant medication
- test article receipt/dispensing/return records
- date of study completion
- reason for early discontinuation of test article or withdrawal from the study, if applicable

The subject record is the eCRF or an external record. The author of an entry in the subject record must be identifiable. The first point of entry is considered to be the source record.

Adverse event notes must be reviewed and initialed by the Investigator.

### 15.3. Trial Registration on ClinicalTrials.gov

This study will be registered on ClinicalTrials.gov based on the following: This study is not an early feasibility study.

## 16. DATA MANAGEMENT

### 16.1. Access to Source Data/Document

The Investigator/Institution will permit trial-related monitoring, audits, IEC/IRB review and regulatory inspection(s) by providing direct access to source data/documents. Should the clinical site be contacted for an audit by an IEC/IRB or regulatory authority, JJVC must be contacted and notified in writing within 24 hours.

### 16.2. Confidentiality of Information

Information concerning the investigational product and patent application processes, scientific data or other pertinent information is confidential and remains the property of JJVC. The Investigator may use this information for the purposes of the study only. It is understood by the Investigator that JJVC will use information developed in this clinical study in connection

# **Clinical Study Protocol**

## **Johnson & Johnson Vision Care, Inc.**

with the development of the investigational product and therefore may disclose it as required to other clinical investigators and to regulatory agencies. In order to allow the use of the information derived from this clinical study, the Investigator understands that he/she has an obligation to provide complete test results and all data developed during this study to the Sponsor.

### **16.3. Data Quality Assurance**

Steps will be taken to ensure the accuracy and reliability of data, include the selection of qualified investigators and appropriate clinical sites and review of protocol procedures with the Principal Investigator. The Principal Investigator, in turn, must ensure that all Sub-Investigators and clinical site personnel are familiar with the protocol and all study-specific procedures and have appropriate knowledge of the study article.

Training on case report form completion will be provided to clinical site personnel before the start of the study. The Sponsor will review case report forms for accuracy and completeness remotely during the conduct of the study, during monitoring visits, and after transmission to data management. Any data discrepancies will be resolved with the Investigator or designee, as appropriate.

Quality Assurance representatives from JJVC may visit clinical sites to review data produced during the study and to access compliance with applicable regulations pertaining to the conduct of clinical trials. The clinical sites will provide direct access to study-related source data/documents and reports for the purpose of monitoring and auditing by JJVC and for inspection by local and regulatory authorities.

### **16.4. Data Monitoring Committee (DMC)**

Not Applicable.

## **17. CLINICAL MONITORING**

The study monitors will maintain close contact with the Principal Investigator and the Investigator's designated clinical site personnel. The monitor's responsibilities will include:

- Ensuring that the investigation is being conducted according to the protocol, any subsequent versions, and regulatory requirements are maintained.
- Ensuring the rights and wellbeing of subjects are protected.
- Ensuring adequate resources, including facilities, laboratories, equipment, and qualified clinical site personnel.
- Ensuring that protocol deviations are documented with corrective action plans, as applicable.
- Ensuring that the clinical site has sufficient test article and supplies.
- Clarifying questions regarding the study.
- Resolving study issues or problems that may arise.
- Reviewing of study records and source documentation verification in accordance with the monitoring plan.

# Clinical Study Protocol

## Johnson & Johnson Vision Care, Inc.

### 18. ETHICAL AND REGULATORY ASPECTS

#### 18.1. Study-Specific Design Considerations

Potential subjects will be fully informed of the risks and requirements of the study and, during the study, subjects will be given any new information that may affect their decision to continue participation. Subjects will be told that their consent to participate in the study is voluntary and may be withdrawn at any time with no reason given and without penalty or loss of benefits to which they would otherwise be entitled. Subjects will only be enrolled if the subject is fully able to understand the risks, benefits, and potential adverse events of the study and provide their consent voluntarily.

#### 18.2. Investigator Responsibility

The Principal Investigator is responsible for ensuring that the clinical study is performed in accordance with the signed agreement, the investigational plan, section 4 of the ICH E6(R2) guidelines on Good Clinical Practice (GCP),Error! Reference source not found. and applicable regulatory requirements. GCP is an international ethical and scientific quality standard for designing, conducting, recording, and reporting studies that involve the participation of human subjects. Compliance with this standard provides public assurance that the rights, safety, and well-being of study subjects are protected, consistent with the principles of the Declaration of Helsinki 64th WMA General Assembly 2013Error! Reference source not found. and that the clinical study data are credible. The Investigator must maintain clinical study files in accordance with section 8 of the ICH E6(R2) guidelines on Good Clinical Practice (GCP),Error! Reference source not found. and applicable regulatory requirements.

